2 STUDY OBJECTIVES

2.1 Primary objective

The primary objective is to compare the volumetric changes in the osseous dimensions following a post-extraction ridge preservation procedure. Three different bone-grafting materials will be used, along with comparison to a non-grafted membrane only group. Data will primarily be obtained from DICOM images acquired by CBCT imaging. A surface based model will be constructed through image segmentation from both the pre- and post-operative CBCT images. The models will then be aligned/superimposed using a surface registration algorithm. Both images will be cropped to represent the same region of interest and the volumes will be calculated and compared.

Hypothesis: No significant differences in ridge volume maintenance are anticipated among the three grafting groups. The combined use of particulate graft material with a resorbable collagen membrane will maintain a greater ridge volume than the use of a resorbable collagen membrane alone.

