A circumferential sulcular incision will be placed around the teeth to be extracted. Periotomes and luxators will be used to extract the tooth with minimal trauma to the adjacent tissues. The socket wall will be examined for any dehiscence greater than 3mm or fenestrations. If these are present, the patient will be excluded from the study. Gauze will be placed in the area to produce wound hemostasis

Immediately following tooth extraction, the patient will have a small field-of-view cone beam computed tomography (CBCT) image produced whilst wearing the radiographic stent. Images will provide pre-preservation data for horizontal and vertical bone locations.

Following CBCT imaging, a ridge preservation procedure will be completed as follows:

- Group A: Symbios demineralized cortical-cancellous granule mix reconstituted in sterile saline will be used to augment the socket and will be covered by a Symbios OsteoShield Collagen resorbable membrane.
- Group B: Symbios OsteoGraf LD-300 reconstituted in sterile saline will be used to augment the socket and will be covered by a Symbios OsteoShield Collagen resorbable membrane.
- Group C: Symbios OsteoGraf/N-300 reconstituted in sterile saline will be used to augment the socket and will be covered by a Symbios OsteoShield Collagen resorbable membrane
- Group D: Socket covered with Symbios OsteoShield Collagen resorbable membrane and no grafting material, allowing socket to heal.

Grafted sockets will be closed with a barrier membrane using 5-0 chromic gut suture. It is anticipated that a cross mattress and/or simple loop sutures will be employed.

All surgical procedures listed above are standard clinical procedures, including preparation and utilization of grafting materials list above.

Post-Surgical Procedures

Buccal and crestal photographs of the surgical site will be obtained, which is standard clinical practice in the School of Dentistry.

Standard UNC post-operative instructions will be given which includes the use of a Chlorhexidine rinse 2 times daily for 2 weeks.

This visit includes a CBCT for research purposes only. The remainder of treatment is standard clinical protocol.

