4.2 Efficacy

4.2.1 Primary outcome variable

4.2.1.1 Volumetric osseous changes

The amount of change in bone volume will be calculated using data from DICOM images acquired by CBCT using 3D software.

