4.2.1.1.1 Methods of assessment

CBCT images will be obtained at baseline (Visit 2) and 3 months following alveolar ridge augmentation (Visit 4). Using 3D imaging software, the bone will be segmented to produce an STL file. Following this, the segmented images will be superimposed and aligned through a fiducial point registration algorithm, and at the same time, the same region of interest will be cropped in each scan and exported as a separate model. The volume of the baseline and 3 month scan will be calculated and compared.

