4.2.1.1.2 Derivation or calculation of variable

The changes in the bone volume between baseline (Visit 2) and 3 months (Visit 4) will be measured electronically using 3D analysis software. The change for each study site will be compared longitudinally and the average for each treatment group will be calculated and compared among treatment and control groups.

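### As written, the primary bone volume mixes what is segmented inside the healed socket with ridge bone loss, so it may not test the ridge-maintenance hypothesis

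*Combined protocol and SAP*

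**What the plan says.** Section 3.1.2 fixes the order of events at Visit 2. The tooth is extracted, the CBCT is taken, and only then is the socket treated: "Following CBCT imaging, a ridge preservation procedure will be completed as follows". The materials are a demineralized allograft (A), a synthetic hydroxyapatite (B), a bovine hydroxyapatite (C), or no graft under the membrane (D).

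Section 4.2.1.1 defines the primary variable: "The amount of change in bone volume will be calculated". Under Section 4.2.1.1.1, "the bone will be segmented to produce an STL file"; the scans are then aligned, the same region is cropped from each, and "The volume of the baseline and 3 month scan will be calculated and compared". Section 4.2.1.1.2 adds: "The changes in the bone volume between baseline (Visit 2) and 3 months (Visit 4) will be measured electronically using 3D analysis software".

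Section 2.1 describes the measurement slightly differently: "A surface based model will be constructed through image segmentation from both the pre- and post-operative CBCT images". It states the hypothesis in terms of the ridge. Among the grafts, "No significant differences in ridge volume maintenance are anticipated among the three grafting groups"; and graft plus membrane "will maintain a greater ridge volume than the use of a resorbable collagen membrane alone".

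No section gives a segmentation threshold, a rule for the open socket at baseline, or a rule for graft particles still present at 3 months.

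**The concern.** An empty socket at baseline contributes nothing to segmented bone. Anything segmented there at 3 months therefore enters the primary variable as gain, whether it is new bone or leftover graft. Outer and crestal resorption enters the same number as loss. The hypothesis concerns the second quantity, while the variable as written is the sum of both.

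This matters because socket content is what is randomised. Section 6.2.1 compares A with B, with C and with D, and in each pair the two arms have different contents. Arms with the same ridge loss could differ on the primary variable, and arms with different ridge loss could look alike. In either case the result would not answer the question in Section 2.1.

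**Working it through.** **Inputs.** From the documents: scan timing (3.1.2), the segmentation, cropping and subtraction (4.2.1.1.1, 4.2.1.1.2), and the planned test (6.2.1). The plan gives no socket volume, fill fraction or threshold, so it has no figure of its own to reproduce on this point. The one figure borrowed is 18 evaluable subjects per group (6.3), and it reproduces. With difference 0.5, SD 0.5, two-sided 0.05 and 80% power, the normal formula gives 2 × (1.96 + 0.842)² = 15.7, so 16. The t-test needs 17 (power 0.807). Dividing by the rank-sum efficiency gives 17/0.955 = 17.8, so 18, and 18/0.90 = 20. That figure is not disputed here.

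**Step 1: what the variable contains.** Let
- W = ridge bone segmented at baseline,
- V = empty socket volume at baseline,
- w = ridge bone lost by 3 months,
- g = material segmented inside the former socket at 3 months,
- v = former socket space that lies outside the ridge contour at 3 months.

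This is simplified: marrow spaces and any bone gained outside the old contour are ignored, and lost bone is taken to lie outside the new contour.

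- Segmented volume: W at baseline and W − w + g at 3 months. Change = g − w.
- Contour volume, both scans closed crest to crest: W + V at baseline and W + V − w − v at 3 months. Change = −(w + v).
- Between two arms, the segmented measure gives (g₁ − g₂) − (w₁ − w₂). The socket term cancels only if g₁ = g₂.

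The two measures do not share one loss term. The contour loses w + v and the segmented volume loses only w. Also, g cannot exceed V − v.

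**Step 2: illustrations.** Every volume here is an assumption. Take V = 150 mm³ and v = 0. Ridge loss is 27 mm³ (0.5 mm over a 6 × 9 mm face) or 54 mm³ (1 mm over the same face). Fill is g = f × V.

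| Case | Arm 1 segmented change | Arm 2 segmented change | Contour change, arm 1 / arm 2 |
|---|---|---|---|
| Equal loss of 27; f = 0.50 vs 0.90 | 75 − 27 = +48 | 135 − 27 = +108 | −27 / −27 |
| Loss 54 vs 27; f = 0.68 vs 0.50 | 102 − 54 = +48 | 75 − 27 = +48 | −54 / −27 |
| Loss 54 vs 27; f = 0.86 vs 0.50 | 129 − 54 = +75 | 75 − 27 = +48 | −54 / −27 |

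The first row creates a 60 mm³ difference from nothing, the second hides a real 27 mm³ difference, and the third reverses it. With equal loss, the false gap is V × (difference in f). This runs from 100 × 0.10 = 10 to 200 × 0.50 = 100 mm³, of either sign, over an assumed range of 100–200 mm³ and 10–50 percentage points.

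**Step 3: closing one scan is not enough.** In the first row, suppose only the baseline scan is capped and the socket is still open at the crest at 3 months. The changes are (0.50 − 1) × 150 − 27 = −102 and (0.90 − 1) × 150 − 27 = −42. The 60 mm³ gap remains.

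**Step 4: effect on the planned test.** This was simulated with 18 per group, normal data and 4,000 replicates. With no difference in ridge loss, a fill difference of 0.25, 0.5 or 1.0 SD of the measured change makes the Wilcoxon test reject 9%, 29% or 80% of the time. With no fill difference it rejects 4%, against a nominal 5%. Which of these fill differences is realistic is not known from the documents.

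**The case against.** The strongest reply is that net bone volume is a legitimate outcome and the one the protocol names. The synopsis speaks of osseous volume change in an extraction socket, and Section 4.2.1.1 speaks of bone volume. If the membrane-only arm forms less bone in the socket, that is a real osseous difference; only residual graft counted as bone is clearly artefact. This stands, and it is why the segmented volume should be kept. It does not make that volume a measure of ridge maintenance.

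A second reply is that the surface based model in Section 2.1 may mean an outer envelope, which would remove the problem. That reading is possible, but no section states it, and the sections that define the variable refer to segmented bone.

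Third, Section 4.2.2.1.2 already measures buccal-to-lingual width at three depths, plus height, largely unaffected by fill. This helps as a cross-check. But those measures are linear and secondary, and Section 1.1 presents reliance on linear measures as the limitation of earlier evidence.

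Fourth, the cubic-millimetre examples rest on assumed inputs. They also take v = 0. If 27 mm³ of the former socket lay outside the new contour in arm 1, fill could not exceed (150 − 27)/150 = 0.82, and the third row, which needs 0.86, could not occur. The examples show a mechanism, not its size.

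**Conclusion.** The concern holds in a limited form. It follows from scan timing and the written derivation that the primary variable adds socket contents to ridge change, while the hypothesis is about the ridge alone. That the two could rank arms differently rests on segmented fill differing between arms, which is plausible because socket content is what is randomised, but is not documented. Neither size nor direction can be derived.

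A reader might infer three stronger conclusions, none of which the documents support:
- *That the protocol contradicts itself.* It is mostly silent. Section 2.1 can be squared with Section 4.2.1.1.1; what is missing is the measurement rule.
- *That a particular arm will be favoured.* Section 3.3.1 says A maintains space and that B and C are suited to resorption, but also that C keeps the space until the patient's bone replaces it. It says nothing about how any material appears on CBCT.
- *That bone volume is the wrong outcome.* Its own wording in the synopsis and Section 4.2.1.1 supports it as an outcome.

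This is an inexpensive improvement, held with medium confidence.

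**What to change.** In Section 4.2.1.1.1, before any scan is measured:
- State that the Section 2.1 hypothesis is tested on the volume inside the outer ridge contour of the same cropped region. Close both scans by the same rule: each is capped from its own buccal crest to its own lingual crest, and everything beneath is filled.
- Fix one segmentation threshold and one residual-graft rule for all arms. The graft rule must cover graft at the crest, because that could set the position of the cap.
- Report the change in segmented bone volume beside the contour volume. Describe it as socket fill plus any residual graft minus bone loss, and do not read it alone as ridge maintenance.
- Align the wording of Sections 2.1 and 4.2.1.1 and the synopsis with these definitions.

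The cost is an extra measurement step on scans already planned and a protocol amendment handled under Section 7.3. The protocol is dated October 4, 2016, and last-subject completion was estimated for Q3 2016, so scans may already exist; the rule should still be fixed before they are measured. The contour volume has its own weakness: it gives no credit for bone fill and counts an unfilled or concave socket as full. That is why both volumes must be reported.

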4.2.1.1.2 Derivation or calculation of variable

The changes in the bone volume between baseline (Visit 2) and 3 months (Visit 4) will be measured electronically using 3D analysis software. The change for each study site will be compared longitudinally and the average for each treatment group will be calculated and compared among treatment and control groups.

4.2.2 Secondary Outcome Variables

4.2.2.1 Osseous dimensional changes

The amount of horizontal and vertical bone changes will be calculated using data from DICOM images acquired by CBCT using 3D software.

4.2.2.1.1 *Methods of assessment*

CBCT images will be obtained at baseline (Visit 2) and 3 months following alveolar ridge augmentation (Visit 4). Using 3D analysis software, the CBCT images will be aligned via superimposition through fiducial point registration, to permit evaluation of bone changes within the bound edentulous space.

4.2.2.1.2 *Derivation or calculation of variable*

The mid-alveolar point (middle of the extraction site) positioned on a tangent drawn from the mesial and distal adjacent tooth CEJs will be used as a reference point for assessment of dimensional bone changes in the Z-axis (Bone width) at 3, 6 and 9mm as measured from the height of the original buccal zenith (with the aid of a radiographic stent. Measurements will be taken from at these points from the buccal plate to the lingual plate. Changes in the Y-axis (bone height) will also be assessed. The changes in the bone dimensions between baseline (Visit 2) and 3 months (Visit 4) will be measured. The change for each study site will be compared longitudinally and the average for each treatment group will be calculated and compared among treatment groups.

4.2.2.2 Soft tissue dimensional change

The amount of soft tissue change will be assessed through the use of dental casts at two time points following extraction and ridge preservation, and 3 months.

4.2.2.2.1 *Methods of assessment*

Elastomeric impressions will be made of the site at baseline, and 3 months following extraction. The impression will be poured in dental stone, and the cast will be scanned using an optical/laser scanner to produce a digitized model. The digital models will then be aligned in 3D software and superimposed on one another and the relevant CBCT image utilizing the fiducial point registration algorithm.

4.2.2.2.2 *Derivation or calculation of variable*

The mid-alveolar point (middle of the extraction site) positioned on a tangent drawn from the mesial and distal adjacent tooth CEJs will be used as a reference point for assessment of dimensional bone changes in the Z-axis (soft tissue width) at 3, 6 and 9mm as measured from the height of the original buccal zenith and indicated on the radiographic stent. Measurements will be taken from at these points from the buccal contour to the underlying buccal plate. Changes in the Y-axis (soft tissue height) will also be assessed. The changes in the soft tissue dimensions between baseline (Visit 2) and 3 months (Visit 4) will be measured. The change for each study site will be compared longitudinally and the average for each treatment group will be calculated and compared among treatment groups.

4.3 Patient reported outcomes

Not applicable

4.4 Health economic measurements and variables

Not applicable

4.5 Pharmacokinetics

Not applicable

4.6 Safety measurements and variables

The methods for collecting safety data are described below.

4.6.1 Adverse Events

4.6.1.1 Definitions

The definitions of AEs, ADEs and Serious Adverse Events (SAEs) are given below. It is of the utmost importance that all staff involved in the study are familiar with the content of this section. The principal investigator is responsible for ensuring this.

Adverse Event

An AE is any untoward and unintended medical occurrence in a subject. This definition does not imply that there is a relationship between the AE and the medical device under investigation. An AE which is possibly related, is one that may have been caused by the medical device, or treatment, however there is insufficient information to determine the likelihood of this possibility.

- Possibly related: temporal relationship of the onset of the event, relative to the use/administration of the medical device, is reasonable but the event could have been due to another, equally likely cause.
- Non-related (unlikely): temporal relationship of the onset of the event, relative to the use/administration of the medical device, is not reasonable or another cause can itself explain the occurrence of the event.

Ambiguous cases should be considered as possibly related.

Adverse Device Effect

An ADE is any untoward and unintended response to a medical device. This definition includes any event resulting from insufficiencies or inadequacies in the instructions for use of the medical device or any event that is a result of a user error. This definition also includes treatment- or procedure-related events. ADEs can only occur from the time of medical device use/administration. Here the event is related to the use of the medical device where there is a probable/definite relationship that the event may have been caused by the medical device, or treatment.

- Probably related: temporal relationship of the onset of the event, relative to the use/administration of the medical device, is reasonable and the event is more likely explained by the medical device/treatment than by any other cause.
- Definitely related: temporal relationship of the onset of the event, relative to the use/administration of the medical device, is reasonable and there is no other cause to explain the event.

Serious Adverse Event

A SAE is an AE/ADE occurring during any study phase of the medical device that fulfills one or more of the following criteria:

- Results in death
- Is immediately life-threatening
- Requires in-subject hospitalization or prolongation of existing hospitalization
- Results in persistent or significant disability or incapacity
- Is a congenital abnormality or birth defect
- Is an important medical event that may jeopardize the subject or may require medical intervention to prevent one of the outcomes listed above

If a non-related AE becomes serious, i.e. fulfilling one or more of the above criteria, action should be taken as for any other SAE.

4.6.1.2 Recording of Adverse Events and Adverse Device Effects

At each visit, scheduled or unscheduled, the subject will be asked an open question; "Have you had any health problems since the previous visit?"

All health problems, reported by the subject or found at the clinic visit, where the investigator believes the event "possibly" has been caused by the investigational medical device or treatment, must be recorded in the CRF as AEs, specifying time of onset, action taken, outcome and whether it constitutes a SAE or not. Non-related AEs must be recorded in the CRF together with a short description and whether it constitutes a SAE or not.

All health problems, reported by the subject or found at the clinic visit, where the investigator believes the event "probably/definitely" has been caused by the investigational medical device or treatment, must be recorded in the CRF as AEs and ADEs, specifying time of onset, action taken, outcome and whether it constitutes a SAE or not.

Should a pregnancy occur, it must be reported in accordance with the procedures described in Section 9.2, Pregnancy. Pregnancy in itself is not regarded as an AE

unless there is a suspicion that a medical device under study may have interfered with the effectiveness of a contraceptive medication.

4.6.1.3 Reporting of Serious Adverse Events

Timelines for reporting of SAEs

Investigators and other study site personnel must inform the ethics committee and, if necessary, the appropriate regulatory authorities of any SAE that occurs during the course of the study within the timeline set by the code of federal regulations.

4.7 Genetics

Not applicable

5 DATA MANAGEMENT

5.1 Data handling

A web-based electronic data capture system (REDCAP) will be used. The eCRF will be completed for each included patient. The completed eCRFs will not be made available in any form to third parties without written permission from the principal investigator/sponsor.

All data from source documents will be entered into the eCRF database. The data entry will be verified by means of double data entry or proofreading. Before database lock, both manual and computerized validation tests will be performed and, if necessary, data queries will be sent to the investigator for clarification. Should questionable data be detected during the validation process, written queries will be raised as result of this validation. The study site personnel are required to resolve any such queries. The eCRFs will be retained for 3 years following completion of the study as required by law and then disposed of according to the standard operating procedure of the School of Dentistry for patient information.

5.2 Record retention

To enable evaluations and/or audits from regulatory agencies, the investigator agrees to keep records in the Investigator's Study File (ISF), including the identification list of the participating patients, all original signed Informed Consent forms, and detailed records of medical device disposition. To comply with international regulations, the investigator should retain the records for 3 years following completion of the study as required by law and then disposed of according to the standard operating procedure of the School of Dentistry for patient information.

6 STATISTICAL METHODS AND DETERMINATION OF SAMPLE SIZE

6.1 Statistical evaluation – general aspects

A comprehensive Statistical Analysis Plan (SAP) may be prepared before database lock. If prepared, the SAP will be kept as an appendix to the Data Management Plan. When using the terminology descriptive statistics it means that number of patients, mean, median, standard deviation, minimum and maximum values will be presented for continuous data and frequencies and percentages for categorical data.

Descriptive statistics will be given for each variable in the study and p-values may be complemented by confidence intervals as appropriate. A p-value less than 0.05 will be considered “statistically significant”.

